#### PROTOCOL SYNOPSIS

[figure not shown]

A Phase 1 Study of the Safety and Tolerability of Single and Multiple Doses of ANK-700 in Patients with Relapsing-Remitting Multiple Sclerosis

# Name of Investigational Product

ANK-700

# Name of Active Ingredient

Approximately 15 sites in the United States (US)

#### Study Period (Years)

Estimated date first patient enrolled:

October 2020

Estimated date last patient completed:

September 2023

# **Phase of Development**

1

#### **Objectives**

- Primary
  - Assess the safety and tolerability of escalating doses of ANK-700 in patients with relapsing-remitting multiple sclerosis (RRMS)
- Secondary
  - Evaluate the pharmacokinetics (PK) of escalating doses of ANK-700 in patients with RRMS

# Methodology

This is a 2-part, multicenter, Phase 1 study of ANK-700 in patients with RRMS. The 2 parts include:

- Part A First-in-human, single ascending dose (SAD) cohorts
- Part B Randomized, double-blind, PBO-controlled, multiple ascending dose (MAD) cohorts

Part A and Part B will be conducted in adult patients (18 to 60 years inclusive, at screening), diagnosed with RRMS, and an EDSS score  $\leq$  6.5. Patients receiving a stable dose of a fumarate drug (i.e., dimethyl fumarate, diroximel fumarate) for  $\geq$  6 months will be allowed to remain on the fumarate drug throughout the study.

A copy of the EDSS is available in Appendix 2.

## Part A – SAD

The SAD part will include up to 3 cohorts of 3 patients each. Patients within each dose cohort will each receive 1 dose of ANK-700 intravenously (IV) and will be monitored for up to 6 months. Patients will be dosed  $\geq$  14 days apart to monitor for acute and subacute reactions. Patients will arrive at the clinic on the morning of dosing (Day 1 [D1]) and will be monitored in the clinic for 8 hours after completion of the ANK-700 infusion for assessment of acute safety and PK blood sample collection. Patients will return to the clinic on D4 $\pm$ 1, D15, D29 $\pm$ 1, and at 3 and 6 months for follow-up. In the event that patients are unable to return to the clinic for protocol-specified visits, alternative methods for safety assessments and data collection may be employed to ensure the safety of the patient where appropriate.

Doses evaluated in Part A will include 0.3 mg/kg (Cohort 1), 1.0 mg/kg (Cohort 2), and 3.0 mg/kg (Cohort 3). After all patients within a given dose cohort have been followed for ≥ 14 days post-dose, a safety review will be performed by the Safety Monitoring Committee (SMC) to review all adverse events (AEs) and available laboratory test and PK data. Initiation of the next higher dose level will commence upon recommendation by the SMC and approval by the Sponsor.

Please see Table 1 for the complete schedule of assessments for Part A.

#### Part B - MAD

The first MAD cohort (Cohort 4) will be initiated after the safety review of SAD Cohort 2, a recommendation to proceed by the SMC, and approval from the Sponsor.

Patients in the MAD cohorts will be randomized 2:1 to either ANK-700 or PBO. Patients will be stratified based upon their use of fumarate medications at study entry within the interactive response technology system. A total of 12 patients will be enrolled per dose cohort (ANK-700, n = 8; PBO, n = 4). Patients will arrive at the clinic on the morning of dosing and will be monitored in-clinic for 8 hours after completion of their first infusion for assessment of acute safety and PK blood sample collection. A total of 3 doses (1 dose every 3 days) will be

administered in Part B, a regimen that was effective in animal models of multiple sclerosis (MS). Patients will return to the clinic on D22, D43, and at 3, 6, and 12 months for follow-up. In the event that patients are unable to return to the clinic for protocol-specified visits, alternative methods for safety assessments and data collection may be employed to ensure the safety of the patient where appropriate.

Doses planned for evaluation in Part B include 0.3 mg/kg (Cohort 4) and 1.0 mg/kg (Cohort 5). Both Part B cohorts will employ sentinel dosing to monitor for the acute and subacute safety of multiple doses of ANK-700. In this design, the first 2 patients in a cohort (1 ANK-700 and 1 PBO) will complete all 3 doses and then complete an additional 14 days of safety monitoring (through D22) before dosing can be initiated in any further patients.

Cohort 5 will only commence after review of the safety, tolerability, and available PK data of all the SAD cohorts (Cohorts 1 to 3) and Cohort 4, recommendation by the SMC, and approval by the Sponsor.

Please see Table 2 for the complete schedule of assessments for Part B.

## **Number of Patients (Planned)**

It is anticipated that the study will enroll approximately 33 to 42 patients across 5 dose cohorts.

Part A (SAD) will enroll approximately 9 to 18 patients across 3 dose cohorts using a 3+3 dose escalation design without intra-patient dose escalation. In Part A, patients may be replaced if they do not receive the full dose of study drug or do not complete the D15 visit, as long as they did not discontinue the study because of dose-limiting toxicity (DLT). No patient with a DLT will be replaced.

Part B (MAD) will enroll approximately 24 patients across 2 dose cohorts. Sixteen patients will receive ANK-700 and 8 patients will receive PBO. In Part B, patients may be replaced if they do not receive all 3 doses and complete the D22 visit, as long as they did not discontinue the study because of a DLT. No patient with a DLT will be replaced.

#### **Starting Dose and Dose Escalation**

The starting dose of ANK-700 will be 0.3 mg/kg based on findings from Good Laboratory Practice (GLP) toxicology studies and animal models in MS, which identified the pharmacologically active doses.

Part A will employ a 3+3 design to evaluate single ascending doses of ANK-700. At any dose level, if none of the first 3 patients dosed experience a DLT within 14 days of treatment, then escalation to the next dose level may proceed if recommended by the SMC and approved by the Sponsor. If 1 of the first 3 patients in the cohort experiences a DLT within 14 days of treatment (D1 to D15), the dose level may expand to a maximum of 6 patients. If no DLT occurs among the additional patients enrolled at that dose level, then escalation to the next dose level may proceed if recommended by the SMC and approved by the Sponsor. The first

MAD cohort (Cohort 4) will be initiated after the safety review of SAD Cohort 2 (Part A), a recommendation to proceed by the SMC, and approval by the Sponsor. Cohort 5 will only commence after review of the safety, tolerability, and available PK data of all the SAD cohorts (Cohorts 1 to 3) and Cohort 4, recommendation by the SMC, and approval by the Sponsor.

DLTs include any Grade 2 AE not resolving within 14 days or any ≥ Grade 3 AE occurring during the dose-escalation safety monitoring period (D1 to D15 in Part A; D1 to D22 in Part B).

Any  $\geq$  Grade 4 AE will result in notification to the Food and Drug Administration (FDA) in parallel with the SMC; all study dosing and enrollment will be paused pending review by the FDA.

The non-tolerated dose (NTD) is the dose level at which > 1 patient experiences a DLT during the dose-escalation safety monitoring period (D1 to D15 in Part A; D1 to D22 in Part B). The maximum tolerated dose (MTD) will be defined as the proximal dose level below the NTD administered during the study. Of note, dose escalation may not identify an NTD or MTD.

## **Safety Monitoring Committee**

This study will utilize an independent SMC that will meet regularly during dose escalation to review all available data, including safety and PK. The SMC will make recommendations concerning dose escalation and/or any changes to the dosing paradigm based on review of the received data. The SMC will also make recommendations about the dose(s) selected for Part B. The final decisions related to dose escalation or the dosing paradigm will be made by the Sponsor.

#### **Inclusion Criteria**

#### Key Inclusion Criteria

- 1. Male or female adults aged 18 to 60 years inclusive at screening
- 2. Diagnosed with RRMS per revised McDonald criteria (2017) with an EDSS score  $\leq$  6.5 at screening
- 3. Neurologically stable with no evidence of relapse within the 28 days before signing the informed consent form (ICF)
  - Note: Patients who experienced relapse during the screening period (i.e., after signing the ICF but before dosing) may be rescreened after 28 days
- 4. Either not currently receiving disease modifying MS therapy, or currently using fumarate drugs (i.e. dimethyl fumarate, diroximel fumarate)
  - Note: Patients on fumarate drugs are only eligible if they have been on a stable dose  $\geq 6$  months before administration of study drug
- 5. Patients must use a highly effective method of birth control or are sterile or postmenopausal as confirmed by study Investigator for the first 3 months (through D90) of the study

6. Patient has signed and understands the ICF

## Key Exclusion Criteria

- 1. Diagnosis of primary progressive MS or secondary progressive MS
- 2. Uncontrolled or significant medical conditions (including active infection, chronic hepatitis, or Neuromyelitis Optica Spectrum Disorder) which, in the opinion of the Investigator, preclude participation
- 3. Has any of the following laboratory parameters at screening:
  - a. Hemoglobin < 10 g/dL
  - b. Platelet count  $< 100 \times 10^9/L$
  - c. White blood cell count outside the normal range and assessed as clinically significant by the Investigator
  - d. Alanine aminotransferase, aspartate aminotransferase, or alkaline phosphatase  $> 1.5 \times$  the upper limit of normal
  - e. Estimated glomerular filtration rate < 60 mL/min/1.73 m² based on the Cockcroft-Gault equation during screening
- 4. Positive for HIV, hepatitis B virus, or hepatitis C virus
- 5. Patients treated with glatiramer acetate, parenteral steroids or adrenocorticotropic hormone, β-interferon, or plasma exchange within the 3 months prior to first dose
- 6. Patients treated with sphingosine-1-phospate receptor modulators such as fingolimod, ozanimod, or siponimod within 6 months prior to first dose
- 7. Patients treated with cytotoxic agents (including, but not limited to, cladribine, mitoxantrone, cyclophosphamide, azathioprine, and methotrexate), laquinimod, teriflunomide, or IV gamma globulin within 12 months prior to first dose
- 8. Patients treated with monoclonal antibody therapy (including natalizumab, daclizumab, rituximab, ofatumumab, and ocrelizumab) within 24 months prior to first dose except anti-severe acute respiratory syndrome coronavirus 2 monoclonal antibodies
- 9. Patients previously treated with alemtuzumab, total lymphoid irradiation, mesenchymal stem cell or hematopoietic stem cell transplantation, or tolerance-inducing therapies for MS
- 10. Patients receiving any vaccination within 28 days prior to first dose
- 11. Patients with clinical signs and symptoms consistent with suspected COVID-19 or confirmed COVID-19 infection by appropriate laboratory test within the last 4 weeks prior to screening or on admission
  - Note: Patients who experienced symptoms consistent with COVID-19 or confirmed infection during the screening period (i.e., after signing the ICF but before dosing) may be rescreened after 4 weeks
- 12. Patients with a prior severe course of COVID-19 requiring extracorporeal membrane oxygenation (ECMO) or mechanical ventilation

- 13. Patient does not agree to limit alcohol intake to 2 drink equivalents or less per day during the study
- 14. Contraindication to or inability to undergo gadolinium-enhanced magnetic resonance imaging (MRI) scan
- 15. Use of any investigational drug or experimental procedure within previous 6 months that would interfere with the assessment of ANK-700
- 16. Patients who are pregnant or breastfeeding

# **Investigational Product, Dosage, and Mode of Administration**

Administration of ANK-700

will be by

IV infusion over approximately 30 minutes. For Part A, patients will receive a single IV infusion of ANK-700. For Part B, patients will receive a total of 3 IV infusions, administered 3 days apart, of either ANK-700 or PBO.

# **Study Duration per Patient**

The maximum duration of study participation for patients in Part A is approximately 210 days, which includes a screening period of up to 28 days, followed by a single dose of ANK-700 on D1, and clinic visits on D4, D15, D29, and at 3 and 6 months.

The maximum duration of study participation for patients in Part B is approximately 393 days, which includes a screening period of up to 28 days, followed by 3 doses of ANK-700 or PBO on D1, D4, and D7, and clinic visits on D22, D43, and at 3, 6, and 12 months.

#### **Assessment of Safety**

Safety will be assessed through the monitoring of AEs, clinical laboratory, vital signs, and physical examination findings, and disease relapse through EDSS and MRI evaluations.

Patients will be monitored continuously for AEs from the signing of the ICF until the final follow-up visit. AE severity will be assessed using the National Cancer Institute Common Terminology Criteria for AEs (NCI-CTCAE) version 5.0 or higher.

In relation to patient safety during the COVID-19 pandemic, current national laws and local recommendations should be strictly adhered to during the study.

Patient safety will be evaluated during Part A (SAD) and Part B (MAD) to determine dose escalation. The dose-escalation safety monitoring period in Part A is from the single IV administration of ANK-700 through the D15 clinic visit. The dose-escalation safety monitoring period in Part B is from the first IV administration of ANK-700 through the D22 clinic visit. In both parts, patients will be monitored in the clinic for AEs for 24 hours after completion of the first IV infusion. In Part B, patients will be monitored in the clinic for AEs for 4 hours after completion of the second and third IV infusion. Any DLT experienced during

the dose-escalation safety monitoring period will result in a pause in the study and review of all the available safety data by the SMC before treating additional patients and/or continuing dose escalation.

# **Primary Endpoint**

• Incidence and severity of treatment-emergent AEs as assessed by the NCI-CTCAE v5.0 or higher

# **Secondary Endpoint**

• Plasma concentrations and PK parameters of ANK-700

#### **Pharmacokinetics**

PK samples will be collected during both Part A and Part B to understand the PK profile of escalating doses of ANK-700 in humans. PK parameters and concentration data will be summarized for Part A and Part B and will be combined for doses with more than 2 patients in each dose group.

In Part A and Part B, samples for PK assessment will be collected according to the schedules outlined in Table 1 and Table 2.

#### **Statistical Methods**

Statistical methods will be descriptive. No hypothesis will be formally tested. For Part A and Part B, summary statistics will be provided by cohort. For Part B only, placebo-treated patient data will be pooled. Categorical variables will be summarized using numbers and percentages. Continuous variables will be summarized by total number (n), mean, standard deviation, median, and range (minimum and maximum).

For the first dose, Part A and Part B will be pooled and summarized for demographic and PK analysis. A formal statistical analysis plan will be developed and finalized before study database lock.

Table 1: Schedule of Assessments Part A (SAD)

Assessment a	Screening	7		Stu	Early Term. b			
Study Day	-28 to 0	1 c	4±1	15	29±1	90±7	182±7	
Screening Assessments								
Informed consent	X							
Medical history/demographics	X							
Disease history	X							
Inclusion/exclusion	X							
ECG	X							
HIV, HBV, HCV testing	X							
Clinical Procedures								
Physical examination d	Xe							X
Pregnancy test	X f	X f,g			VC			
Vital signs h	X	Xg		X				X
Concomitant medications and procedures	X	X	X	X	X	X	X	X
EDSS i	X	Xg		X		X	X	
Safety Assessments								
Adverse events	X	X	X	X	X	X	X	X
Laboratory tests (safety)	X	Xg	X	X				X
MRI i	X j			Xk				
Study Drug Administration								
ANK-700 administration		X m						
Additional Blood Samples		•			7	•		
PK blood sample		$\mathbf{X}^{1}$	X					
ADA samples		Xg			X			X
						25		

# Study ANK-700-01 in Relapsing-Remitting Multiple Sclerosis

a All patients should be contacted by site staff 1 day prior to each study visit for assessment of COVID-19 signs and symptoms.

- b Early termination visit only if patient discontinues within 28 days of dosing.
- c On D1 patients will be observed in the clinic/hospital unit for 8h after completion of IV infusion and followed up with by phone following discharge 24 hours after dosing.
- d Additional PEs will also be conducted as clinically indicated.
- e Includes weight at screening only.
- f Pregnancy test at screening must be serum; serum or urine tests are acceptable on Day 1 (D1) prior to dosing. Screening and D1 pregnancy test must be negative before ANK-700 is administered. Additional pregnancy monitoring per local guidelines may be implemented.
- g Samples/measurements to be taken pre-dose.
- h Vital signs include pulse rate, temperature, and diastolic and systolic blood pressure.
- i In the event of a suspected disease relapse, an unscheduled MRI and EDSS assessment may be performed if deemed clinically necessary.
- j The screening MRI must be performed ≥ 10 days prior to dosing on D1. For re-screening, the MRI only needs to be repeated if the previous assessment has been completed >3 months of scheduled dosing or if a relapse has occurred since last assessment.
- k The MRI at D15 may be performed up to 3 days before the D15 Visit.
- One PK sample will be taken pre-dose (≥at least 5 min prior to infusion), with all subsequent PK samples taken after the end-of-infusion (EOI) at the following time points: EOI 0 (+2) min, EOI 7 (±2) min, EOI 15 (±2) min, EOI 30 (±5) min, EOI 1 h (±5 min), EOI 2 h (±5 min), EOI 3 h (±5 min), EOI 4 h (±5 min), EOI 6 h (±5 min), and EOI 8 h (±5 min). PK samples to be taken from the arm that did not receive the infusion. The exact date and time of each sample collection must be recorded for all collected samples.
- m The prepared saline bag and infusion line should be weighed before and after administration. These weights should be recorded using any available scale with a precision to at least one tenth of a gram (0.1 grams). Both weight measurements should be conducted using the same scale to reduce variability.

Abbreviations: ADA = anti-drug antibodies; D=day; Early Term = early terminate	tion; ECG = electrocardiogram;
EDSS = Expanded Disability Status Scale;	t; h = hours; EOI =
end of infusion; HBV = hepatitis B virus; HCV = hepatitis C virus;	; min =
minute; MRI = magnetic resonance imaging;	; PE = physical
examination; PK = pharmacokinetics; SAD = single ascending dose.	to disconditi

Table 2: Schedule of Assessments Part B (MAD) COHORT 4 ONLY

Assessments a	sments a Screening Treatment Period Study Period			10.57	Early Term. b					
Study Day	-28 to 0	1 c	4	7	22	43±2	90±7	182±7	365±14	
Screening Assessments	Screening Assessments									
Informed consent	X					9		3	4	
Medical history/demographics	X			3		51				,
Disease history	X							2, 3		
Inclusion/exclusion	X									
ECG	X					0.8 e	203 SI	203 20 207 70	. 15 . 15	e.
HIV, HBV, HCV testing	X									
Clinical Procedures		*				36. Y	34 3	59. 8	37.	
Physical examination d	Xe									X
Pregnancy test	Xf	$X^{f,g}$	$X^{f,g}$	$X^{f,g}$						
Vital signs h	X	Xg			X					
Concomitant medications and procedures	X	X	X	X	X	X	Х	X	X	X
EDSS i	X	Xg			X		X	X	X	
Safety Assessments									l.	M)
Adverse events		X	X	X	X	X	X	X	X	X
Laboratory tests (safety)	X	Xg	Xg	Xg	X					X
MRI i	$\mathbf{X}^{\mathbf{j}}$				$X^k$		$X^1$			
Study Drug Administration						30.	3.		•	
Randomization		X								
ANK-700 or PBO administration		X m,q	X n,q	X o,q						
Additional Blood Samples							•			
PK blood sample		Xº	Xg	$X^p$	X					
ADA samples		Xg			X		X	X	X	X
						US 8	203	203 80		
										5,0
76 <del></del>										

# Study ANK-700-01 in Relapsing-Remitting Multiple Sclerosis

a All patients should be contacted by site staff 1 day before each study visit for assessment of COVID-19 signs and symptoms.

- b Early termination visit only if patient discontinues within 28 days of dosing.
- c On D1 patients will be observed in the clinic/hospital unit for 8h after completion of IV infusion and followed up with by phone following discharge 24 hours after dosing.
- d Pes will also be conducted on study as clinically indicated.
- e Includes weight at screening only.
- f Pregnancy test at screening must be serum; serum or urine tests are acceptable on D1, D4, and D7 prior to dosing. Screening and dosing day pregnancy tests must be negative before study drug is administered. Additional pregnancy monitoring per local guidelines may be implemented.
- g Samples/measurements taken pre-dose.
- h Vital signs include pulse rate, temperature, and diastolic and systolic blood pressure.
- i In the event of a suspected disease relapse, an unscheduled MRI and EDSS assessment may be performed if deemed clinically necessary.
- j The screening MRI must be performed ≥ 10 days prior to dosing on D1. For re-screening, the MRI only needs to be repeated if the previous assessment has been completed >3 months of scheduled dosing or if a relapse has occurred since last assessment
- k The MRI at D22 may be performed up to 3 days before the D22 visit.
-  The MRI at D90 may be performed within 2 weeks of the scheduled D90 visit.
- m On D1, patients will be observed in the clinic for 8 h after completion of IV infusion.
- n On D4 and D7, patients will be observed for 4 h after completion of IV infusion.
- o On D1, 1 PK sample will be taken pre-dose (≥ 5 min prior to infusion), with all subsequent PK samples taken after the end of infusion (EOI) at the following time points: EOI 0 (+2) min, EOI 7 (±2) min, EOI 15 (±2) min, EOI 30 (±5) min, EOI 1 h (±5 min), EOI 2 h (±5 min), EOI 3 h (±5 min), EOI 4 h (±5 min), EOI 6 h (±5 min) and EOI 8 h (±5 min). PK samples to be taken from the arm that did not receive the infusion. The exact date and time of each sample collection must be recorded for all collected samples.
- P On D7, PK samples to be taken at pre-dose (≥ 5 min prior to infusion), and the following time points after the end of infusion (EOI): EOI 0 (+ 2) min, EOI 7 (± 2) min, EOI 15 (± 2) min, EOI 30 (± 5) min, EOI 1 h (± 5 min), EOI 2 h (± 5 min), EOI 3 h (± 5 min), and EOI 4 h (± 5 min). PK samples to be taken from the arm that did not receive the infusion. The exact date and time of each sample collection must be recorded for all collected samples.
- q The prepared saline bag and infusion line should be weighed before and after administration. These weights should be recorded using any available scale with a precision to at least one tenth of a gram (0.1 grams). Both weight measurements should be conducted using the same scale to reduce variability.

Abbreviations: ADA = anti-drug antibodies; D = day; Early Term = early te	rmination; ECG = electrocardiogram;
EDSS = Expanded Disability Status Scale;	; EOI = end of
infusion; h = hours; HBV = hepatitis B virus; HCV = hepatitis C virus;	Vest
IV = intravenous; MAD = multiple ascending dose; min = minutes; MRI =	magnetic resonance imaging;
PBO = placebo; PD = pharmacodynamics; PK = pharmacokinetics;	

Table 3: Schedule of Assessments Part B (MAD) COHORT 5 ONLY

Assessments a	Screening	ng Treatment Period Study Period		Study Period			Early Term. b			
Study Day	-28 to 0	1 c	4	7	22	43±2	90±7	182±7	365±14	
Screening Assessments								-7		
Informed consent	X			8				- 2,	4	
Medical history/demographics	X									
Disease history	X			8			2, ,	2, 3		
Inclusion/exclusion	X									
ECG	X				5 7 S	(B) (B)	203 8	305 81 167 W	(B	E S
HIV, HBV, HCV testing	X									
Clinical Procedures									×6.	
Physical examination d	Xe									X
Pregnancy test	$X^f$	$X^{f,g}$	$X^{f,g}$	X f,g						
Vital signs h	X	Xg			X	100				**
Concomitant medications and procedures	X	Х	X	X	X	X	х	Х	X	X
EDSS i	X	Xg			X		X	X	X	
Safety Assessments									le:	
Adverse events		X	X	X	X	X	X	X	X	X
Laboratory tests (safety)	X	Xg	Xg	Xg	X					X
MRI i	$\mathbf{X}^{\mathbf{j}}$				Xk		X 			
Study Drug Administration						di i		500. 10	cd.	
Randomization		X								
ANK-700 or PBO administration		X m,r	X n,r	X o,r		112 51	314	50 50	10	
Additional Blood Samples										
PK blood sample		Xº	Xg	$X^p$	X					
ADA samples		Xg			X		X	X	X	X
			3		7	GS - 81		30.5	25	
70 :: 3										

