# 3. ENDPOINTS

# 3.1. PRIMARY ENDPOINT

• Incidence and severity of treatment-emergent adverse events (TEAEs) as assessed by the National Cancer Institute Common Terminology Criteria for Adverse Events (NCI-CTCAE) v5.0 or higher

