# 6.1.5. Expanded Disability Status Scale (EDSS) Assessment

Assessment of EDSS score will be captured at the time points specified in the Schedule of Assessments (Table 1 and Table 2). The EDSS is based on a standard neurological examination, incorporating the pyramidal, cerebellar, brainstem, sensory, bowel/bladder, visual, and cerebral [or mental] functional systems, and ambulation, rated and scored as functional system scores. The EDSS is a disability scale that ranges in 0.5-point steps from 0 (normal) to 10 (death) (Kurtzke 1983). The EDSS must be administered by a certified examiner. All patients with new

Study ANK-700-01 in Relapsing-Remitting Multiple Sclerosis

neurological symptoms suggestive of relapse may have an EDSS assessment performed during an unscheduled visit, if appropriate (see Section 11.1.2).

If the screening EDSS has been completed within 3 months of scheduled dosing it would not need to be repeated as long as the screen fail is not due to MS relapse. If the patient needs to rescreen due to experiencing an MS relapse during the screening period, the patient must wait at least 28 days from the relapse resolution and then a new screening EDSS should be obtained.

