### 6.1.15. Adverse Events

All AEs should be captured on the source documentation and eCRF from the time of signing of ICF through the final Follow-Up Visit/phone call. AEs leading to treatment discontinuation and those considered at least possibly related to ANK-700 should be followed until resolution, return to baseline, or deemed chronic or stable.

All serious adverse events (SAEs) will be immediately reported to the Sponsor from the time of signing the ICF through the Follow-Up Visit/phone call or until the patient has been deemed to be a screen failure. After completion of the AE reporting period (i.e., through the final Follow-Up Visit/phone call), only SAEs attributed to ANK-700 must be reported to the Sponsor.

See Section 11.2 for a full description of the collection and reporting of AEs during this study.

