# 11.1.2. Protocol-Defined MS Relapse

Patients who present with suspected clinical relapse should be assessed by EDSS and/or MRI (with and without contrast and may include spinal cord), as appropriate. Protocol-defined MS relapse for this study is:

• Sudden episode of new symptoms or worsening existing MS symptoms that lasts for ≥ 24 hours and occurs ≥ 30 days after conclusion of previous relapse (patient must be stable or improving for the 30 days immediately preceding relapse) and for which there is no other cause such as infection or environmental triggers. Episodic spasms, sexual dysfunction, fatigue, mood change, or bladder or bowel urgency or incontinence will not suffice to establish the diagnosis of a relapse.

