#### 10. DATA HANDLING AND MISSING DATA

All missing or partial data will be presented in the patient data listing, as they are recorded on the eCRF. Patients lost to follow-up or withdrawn will be included in statistical analyses up to the point of their last evaluation.

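### No closing contact is defined for patients who leave the study after day 28, and the early termination visit omits EDSS, so non-serious AEs and disability at exit may be under-recorded

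*Protocol*

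**What the plan says.** Footnote b, identical in Protocol Tables 1, 2 and 3 and in the three SAP Appendix 1 tables, states: "Early termination visit only if patient discontinues within 28 days of dosing". In the visible rows, the early termination column marks physical examination, concomitant medications, AEs, laboratory tests and ADA, with vital signs in Part A only. The EDSS and MRI cells are blank in that column.

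The primary endpoint (Protocol 3.1) is "Incidence and severity of treatment-emergent adverse events (TEAEs) as assessed by the National Cancer Institute" criteria. AEs are to be captured "from the time of signing of ICF through the final Follow-Up Visit/phone call" (Protocol 6.1.15), and Protocol 6.2 places the final follow-up visit at D182 in Part A and D365 in Part B. The synopsis counts "disease relapse through EDSS and MRI evaluations" among the safety assessments. Protocol 6.1.5 says "Assessment of EDSS score will be captured at the time points specified in the Schedule of Assessments".

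For a possible relapse, footnote i says "In the event of a suspected disease relapse, an unscheduled MRI and EDSS assessment may be performed if deemed clinically necessary", while Protocol 11.1.2 says "Patients who present with suspected clinical relapse should be assessed by EDSS and/or MRI". For patients who leave, SAP Section 10 says "Patients lost to follow-up or withdrawn will be included in statistical analyses up to the point of their last evaluation".

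**The concern.** The period over which TEAEs are counted is far longer than the period in which a departing patient is offered a closing visit. Protocol 11.2.1 has the investigator review, at each protocol-required visit, the AEs since the previous one. After day 28 a withdrawing patient has no further required visit. Protocol 4.10 exempts premature withdrawals from the final follow-up, and Protocol 4.11 lists reasons for withdrawal but gives no exit procedure.

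This matters because disease worsening is a recognised hazard here. Protocol 1.2 reports that earlier work with altered peptide ligands saw exacerbation of disease or more inflammatory lesions, and Protocol 11.1.1 counts worsening of MS as an AE. A treated patient stays in the All-Treated Analysis Set, and so in the denominator, whether or not the last weeks before exit were asked about. With 8 patients in each Part B group, one patient whose only event is missed changes that group's proportion by 1/8 = 12.5 percentage points.

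**Working it through.** **Follow-up length.** The plan's participation figures reproduce from its own schedule. Part A is 28 days of screening + 182 = 210 days, and Part B is 28 + 365 = 393 days. Both match the synopsis and Protocol 13.9.

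**Share of post-dose follow-up with no early termination visit.** With D1 as the dosing day, post-dose follow-up is (last day − 1) days, and the uncovered part is what remains after the 28-day window.

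| | Post-dose days | Covered to | Uncovered | Share |
|---|---|---|---|---|
| Part A | 182 − 1 = 181 | 28 days | 181 − 28 = 153 | 153/181 = 84.5% |
| Part B, counted from D1 | 365 − 1 = 364 | 28 days | 364 − 28 = 336 | 336/364 = 92.3% |
| Part B, counted from the D7 dose | 364 | 6 + 28 = 34 days | 364 − 34 = 330 | 330/364 = 90.7% |

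Part B has two rows because footnote b does not say which of the three doses starts the 28 days.

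**Gaps between scheduled visits after the window.** These bound how long before exit a patient may have gone without an AE review, if no visit was missed.
- Part B visits at D43, D90, D182 and D365 give gaps of 90 − 43 = 47, 182 − 90 = 92 and 365 − 182 = 183 days.
- Part A visits at D29, D90 and D182 give gaps of 90 − 29 = 61 and 182 − 90 = 92 days.
- Example: a Part B patient who withdraws at D170 was last seen at D90, leaving 170 − 90 = 80 days with no scheduled review.

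**Gaps between scheduled EDSS assessments.**
- Part A (D1, D15, D90, D182): 14, 75 and 92 days.
- Part B (D1, D22, D90, D182, D365): 21, 68, 92 and 183 days.
- A patient who leaves before D15 in Part A or D22 in Part B has only the pre-dose EDSS, because the early termination visit does not repeat it. Such a patient may also be replaced if the discontinuation was not due to a DLT (Protocol 4.1 and 4.2).

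**How many patients this could touch.** The documents give no withdrawal rate, so this is an assumption. For the 24 Part B patients, expected withdrawals are 24 × rate and P(at least one) = 1 − (1 − rate)^24.
- 5%: 1.2 expected, P = 0.71
- 10%: 2.4 expected, P = 0.92
- 20%: 4.8 expected, P = 0.995

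These count withdrawals at any time, so withdrawals after day 28 would be no more than this.

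**Does other text supply the missing contact?**
- Dosing ends on D1 in Part A and D7 in Part B, so a discontinuation after day 28 is a withdrawal from the study. The rule in Protocol 4.10 that follows AEs leading to discontinuation of ANK-700 will rarely apply.
- The provision for other means of assessment (Protocol 4.1 and 4.2) is for patients unable to reach a scheduled visit. It does not mention patients who have withdrawn.
- Protocol 6.1.15 mentions a phone call as an end point for AE capture, but no schedule or section assigns one to a patient who withdraws late.

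**The case against.** A reader might infer that patients who leave because of neurological worsening go unmeasured for the primary safety objective. The documents do not support that. The primary endpoint is TEAEs, not EDSS. AEs are monitored continuously, worsening of MS is an AE, and patients are told to report all AEs. SAEs must be reported within 24 hours of the investigator learning of them. A patient leaving at D10 does get an early termination visit, with AE review, laboratory tests and a physical examination that has a neurological component (Protocol 6.1.6). Protocol 11.1.2 recommends EDSS and/or MRI for a suspected relapse, with no 28-day limit.

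A reader might also infer that SAP Section 10 discards events in withdrawn patients. It does not. It keeps their data up to the last evaluation, and SAP 8.8.1 tabulates and lists TEAEs leading to study discontinuation, so an AE recorded as the reason for leaving has a planned output.

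Nor is bias in favour of ANK-700 established. Relapse is not a withdrawal criterion, corticosteroids are permitted for it, and other disease-modifying therapies are allowed once the D90 visit is complete. Wanting such a therapy cannot readily explain exits in the 92- and 183-day gaps. The calendar shares and gaps measure exposure to the problem, not bias. The 28-day window also extends beyond the D15 and D22 DLT periods, so escalation decisions are largely covered.

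These points narrow the concern without removing it. Spontaneous reporting and SAE rules work only if the site hears of the event. The relapse provisions need a suspected relapse: footnote i is permissive, and Section 11.1.2 can be met by MRI alone. Gradual worsening, and non-serious AEs in the last weeks before a late exit, still have no defined collection point.

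**Conclusion.** The gap is real but limited. After day 28, a patient leaving the study has no defined point at which non-serious AEs and concomitant or disease-modifying therapy since the last visit are collected. That applies to 84.5% of post-dose follow-up in Part A and 90.7 to 92.3% in Part B, depending on which Part B dose starts the 28 days. Disability at exit rests on a discretionary or relapse-triggered assessment at any time, and patients leaving before D15 or D22 have no scheduled post-dose EDSS.

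The consequence is possible under-ascertainment before late exit. Its size depends on an unstated withdrawal rate and on how many events sites would miss. Differential bias between ANK-700 and placebo is possible but not shown, and nothing here invalidates a descriptive TEAE analysis. The change is worth making because it is cheap and the groups are small.

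**What to change.** Amend footnote b in Protocol Tables 1 to 3 and SAP Appendix 1 so that a closing contact is sought from any patient withdrawing from the study before D182 (Part A) or D365 (Part B). It should cover AEs and concomitant or disease-modifying therapy since the last visit, and may be by phone if the patient will not attend. Mark EDSS in the early termination column for patients who attend in person. Laboratory tests and ADA may stay limited to the first 28 days; for Part B, state which dose starts that count. Align footnote i with Protocol 11.1.2, which differ in how firmly they call for assessment of a suspected relapse.

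The cost is one footnote, one table cell and one contact per withdrawing patient. For those who attend, it adds an EDSS by the certified examiner the trial already uses. The sample size and planned analyses do not change.
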